6.3 Subject Selection

The inclusion and exclusion criteria are consistent with recommendations of the European Society of Cardiology,¹ American College of Cardiology, American Heart Association, and the Heart Rhythm Society.² Additionally, sponsor has included investigator input.

Clinical Investigation Plan

Eligibility for implant is based on conformance to all prospectively defined inclusion and exclusion criteria.

6.3.1 Inclusion Criteria

Eligible subjects will meet **all** of the following.

1. Subject must have one of the clinical indications before device implant in adherence with Medicare, ACC/AHA/HRS/ESC single chamber pacing guidelines including:
 - Chronic and/or permanent atrial fibrillation with 2 or 3° AV or bifascicular bundle branch block (BBB block), including slow ventricular rates (with or without medication) associated with atrial fibrillation; or
 - Normal sinus rhythm with 2 or 3° AV or BBB block and a low level of physical activity or short expected lifespan (but at least one year); or
 - Sinus bradycardia with infrequent pauses or unexplained syncope with EP findings; and
2. Subject is ≥ 18 years of age; and
3. Subject has a life expectancy of at least one year; and
4. Subject is not be enrolled in another clinical investigation; and
5. Subject is willing to comply with clinical investigation procedures and agrees to return for all required follow-up visits, tests, and exams; and
6. Subject has been informed of the nature of the study, agrees to its provisions and has provided a signed written informed consent, approved by the IRB; and
7. Subject is not pregnant and does not plan to get pregnant during the course of the study.

6.3.2 Exclusion Criteria

Subjects will be excluded if they meet **any** of the following.

1. Subject has known pacemaker syndrome, has retrograde VA conduction, or suffers a drop in arterial blood pressure with the onset of ventricular pacing; or
2. Subject is allergic or hypersensitive to < 1 mg of dexamethasone sodium phosphate (DSP);
3. Subject has a mechanical tricuspid valve prosthesis; or
4. Subject has a pre-existing endocardial pacing or defibrillation leads; or
5. Subject has current implantation of either conventional or subcutaneous implantable cardioverter defibrillator (ICD) or cardiac resynchronization therapy (CRT) device; or
6. Subject has an implanted vena cava filter; or
7. Subject has evidence of thrombosis in one of the veins used for access during the procedure; or
8. *Subject had recent cardiovascular or peripheral vascular surgery within 30 days of enrollment; or
9. Subject has an implanted leadless cardiac pacemaker

Clinical Investigation Plan

*Recent cardiovascular or peripheral vascular surgery within 30 days of enrollment is defined as the following:

- **Percutaneous valvular correction \leq 30 days**
- **Femoral or abdominal vascular procedure involving incisional access \leq 30 days**
- **Peripheral arterial endovascular procedure or surgery \leq 30 days**
- **Cardiac surgery \leq 72 hrs with ongoing complications, ongoing mediastinal drainage, or re-do sternotomy attributed to bleeding \leq 30 days**
- **Tricuspid valve replacement or annuloplasty \leq 30 days**
- **Any endovascular procedure with specified complication \leq 30 days**
 - **Femoral access site-vascular complication including hematoma requiring transfusion, surgical intervention or prolongation of hospitalization, arterio-venous fistula, pseudoaneurysm or tear**
 - **New pericardial effusion more than trivial/mild, or requiring percutaneous/surgical drainage**
- **Acute deep venous thrombosis**

6.4 . Study Procedures

This section provides a description of all the clinical-investigation-related procedures that subjects undergo during the clinical investigation. **Figure 1** illustrates study flow and **Table 1** lists a summary of scheduled assessments. Refer to **Figure 1** and **Table 1** for an overview of the required study procedures at each interval or study visit.

[figure not shown]
The clinical-investigation-related procedures do not require additional radiation compared to a traditional VVIR lead implant and conform to standard of care for pacemaker patient management with the exception of the following:

- Femoral vein access instead of subclavian vein access
- Addition of Treadmill tests
- Addition of 24 hour Holter monitor

Sponsor representatives may assist the investigator in assessing pacemaker effectiveness (for example pacing, sensing, and rate response effectiveness), downloading diagnostic information and programming pacemaker parameters. Sponsor representatives may also assist the team in equipment setup prior to and during a procedure.

Clinical Investigation Plan

Figure 1: Study Flow Diagram

Clinical Investigation Plan

6.4.1 Enrollment Requirements

6.4.1.1 Recruitment and Enrollment

Candidates for this clinical investigation include patients indicated for a VVI(R) pacemaker. Pre-enrollment records will include evidence of diagnosis indicating need for VVI(R) pacemaker. For the Leadless II study, it is the sponsor's intention that the enrolled subject population be as representative as possible of the eligible population. Physician investigators are strongly encouraged to evaluate all consecutive eligible subjects for participation in the study and, if inclusion and exclusion criteria are met, to approach all eligible subjects, regardless of gender. Centers will be selected for participation in the study based on their ability to screen and enroll eligible subjects, and perform the required study procedures.

Screen subjects as outlined by the inclusion/exclusion criteria. Obtain informed consent from the subject. Collect data on the subject, including gender, age, ethnicity, race, cardiac disease history, cardiac medications (beta blockers, ACE, ARB, anti-platelets, anti-arrhythmics, anti-coagulants), arrhythmia history, and indication for pacemaker implant. Subjects who sign an IRB-approved informed consent and have an attempted or successful implant will be considered enrolled in the study.

Once eligibility screening is completed, subject provides informed consent, and the investigator implants the Nanostim™ LP—or attempts to implant—complete and submit the forms listed under the Implant Procedures to sponsor.

6.4.1.2 Subject Numbering

An identification (ID) number will identify enrolled subjects. The format of this ID number is a combination of the study number, subject number assigned by SJM and a subject ID assigned by the site.

6.4.2 Baseline Assessment

Investigator will record subject's medical history on the Enrollment Form. Investigator will record specific cardiac medications (beta blockers, ACE, ARB, anti-coagulants, anti-platelets, anti-arrhythmics) given to the subject during the same hospital stay as the procedure, as well as during the follow-up period. All subjects will undergo standard laboratory assessment per site's standard of care. For female subjects of childbearing age, investigator will document a pregnancy assessment, which may include a obtaining a blood sample for conducting a pregnancy test.

Clinical Investigation Plan

Investigator will not start any study-specific procedures or alterations of patient care until the informed consent process has been completed and investigator obtains a signed Informed Consent Form.

6.4.2.1 Medications

Investigator will administer all medications per hospital standard of care for pacemaker implant and femoral venous catheterization procedures. Use of anticoagulation medications is not required with the implantation of the Nanostim™ LP. Investigator will record beta blockers, ACE, ARB, anti-coagulants, anti-platelets, anti-arrhythmics given during procedure.

6.4.3 Implant Procedure

6.4.3.1 Femoral Vein Assessment and Access

Turi (2005, 2008), Abu-Fadel *et al* (2009), Seto *et al* (2010), and Fitts *et al* (2008) have shown that physicians can minimize access-site complications by using ultrasound guidance or fluoroscopic guidance when accessing vessels in the groin.³⁻⁷ Although sponsor supports using either technique for assessing femoral vein access-site location, size and presence of disease, investigator will use medical judgment and follow institutional standard of care when accessing the femoral vein during catheter-based procedures.

The ideal puncture site should be located **below the inguinal ligament and above the bifurcation** (Refer to Figure 2).^{5,8-10} Penetrate the skin and puncture the femoral vein using the Seldinger technique. Due to the introducer sheath size, investigator may need to “nick and spread” the tissue at the access-site location to allow for easier transition of the introducer sheath through the tissue tract.

Clinical Investigation Plan

[figure not shown]

Figure 2. Location of femoral vein in relation to femoral artery, inguinal ligament and femoral head

6.4.3.2 Nanostim™ LP Preparation and Implant

Investigator will prepare and implant the Nanostim™ LP in accordance with the manufacturer's instructions for use (IFU). Consult the IFU for implantation guidelines and general handling information. Only approved investigators will be responsible for performing the implant procedure, including placement of the Nanostim™ LP. Investigator will follow standard institutional catheter-based and pacemaker-lead implantation procedures, guidelines, and precautions.

6.4.3.3 Nanostim™ LP Assessment and Programming

Investigator and/or sponsor will interrogate the Nanostim™ LP using the market-approved St. Jude Medical™ Merlin™ Patient Care System (Model 3650) with the Nanostim™ Programmer Link. Investigator will measure and record the following parameters.

- Capture threshold at (0.4 msec)*
- Impedance*
- R-wave amplitude*
- Battery voltage and Estimated time to RRT
- Cumulative paced and sensed event counters

* R-wave amplitude measurements are not required if the subject's intrinsic rate has been established to be below 30 beats per minute. Capture thresholds are not required if a high

Clinical Investigation Plan

ventricular rate is present. Confirm at least three consecutive beats have capture before recording the capture threshold results.

**For subjects implanted with the Nanostim™ LP (Model S1DLCP)-Impedance measurements should not be done because performing this commanded measurement in a device with a high resistance battery can render the device immediately non-functional.*

To avoid potential complications associated with under-sensing, Investigator shall program a sensing margin of at least two times the intrinsic cardiac amplitude (e.g., for an intrinsic R-wave of 4 mV, program the R-sensitivity ≤ 2 mV).

To avoid potential complications associated with loss of pacing capture, Investigator shall maintain pulse amplitude margin of at least two times the pacing threshold (e.g., for a pacing threshold of 0.5V, program the pulse amplitude ≥ 1.0 V).

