6.2.1.2 Primary Effectiveness Endpoint

The composite primary effectiveness endpoint will be used to evaluate pacing thresholds and R-wave amplitudes at the 6-month visit and to document the percentage of subjects with acceptable sensing and pacing performance. Pacing thresholds and R-wave amplitudes will be collected, tabulated for each visit, and also displayed as frequency plots. Acceptable ranges for sensing and pacing are shown in the table below.

Table 2: Acceptable Ranges for Sensing and Pacing

Parameter	Acceptable test values
Pacing voltage	Pacing threshold < 2.0 V at 0.4 ms
R Sensitivity	R-wave amplitude > 5.0 mV or > value at implant

Success Criteria: A subject will be considered to have met the primary effectiveness endpoint if the pacing threshold voltage is \leq 2.0 V at 0.4 ms and the sensed R-wave amplitude is either \geq 5.0 mV at the 6-month visit or \geq the value at implant.

[REDACTED]

[REDACTED]

Clinical Investigation Plan

The inability to sense or pace within the programmable range available in the Nanostim™ LP device, resulting in device repositioning, replacement, or removal will be captured in the associated safety endpoints.

Primary Effectiveness Endpoint Evaluation at 6 Months

H_0 : Rate $\leq 85.0\%$ vs. H_1 : Rate $> 85.0\%$

A sample size of 300 subjects [REDACTED] establishing a two-sided 95% confidence interval for conformance with the above-referenced criteria for pacing threshold and R-wave amplitude, with a lower bound exceeding 85.0%, based on an exact binomial distribution.

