- Healthcare Utilization Form, if applicable

6.4.5.4 3-Month Visit

All subjects will return to the investigation site for a 90-day (± 30 days) follow-up visit. During this visit, investigation team will:

- Assess for adverse events and deviations from investigation plan;
- Assess for changes in beta blockers, ACE, ARB, anti-coagulants, anti-platelets, anti-arrhythmics ;
- Measure and record Nanostim™ LP performance, as described in 6.4.3.3 Nanostim™ LP Assessment and Programming;
- Program Nanostim™ LP and adjust programmable parameters of Nanostim™ LP, as needed;
- Holter Data Collection³
 - Connect each capable subject to 24-hour Holter monitor (until 30 subjects contribute to the analysis); set Nanostim™ LP to **VVIR** mode, if indicated (This test may be performed between 3 and 6 months post-implant).
- CAEP Protocol⁴
 - Administer CAEP protocol (until 30 subjects contribute to the analysis); with rate-response feature in **VVIR ON** mode (refer to CAEP protocol – this test may be performed between 3 and 6 months post-implant).
 - After completing CAEP protocol, program Nanostim™ LP and adjust programmable parameters of Nanostim™ LP, as needed.

Data Submission

Complete and submit the following case report forms and device print outs to St. Jude Medical, Sylmar, CA using the EDC system.

- Follow-up Visit Form (includes medication changes)
- Nanostim™ LP Assessment and Programming Form
- EQ-5D patient survey
- Medications, if any changes
- Study Withdrawal Form, if applicable

³ Holter data collection can be done any time between the 3-month and 6-month follow-up visit.

⁴ Administration of the CAEP protocol can be done any time between the 3-month and 6-month follow-up visit, (until 30 subjects contribute to the analysis).

Clinical Investigation Plan

- Adverse Event Form, if applicable
- Deviation Form, if applicable
- Graded Exercise Test Form, if applicable
- Product Out of Service Form, if applicable
- System Revision Form, if applicable
- Death Form, if applicable
- Healthcare Utilization Form, if applicable

6.4.5.5 6-Month Follow-up Visit

All subjects will return to the investigation site for a 180-day (± 30 days) follow-up visit. During this visit, investigation team will:

- Assess for adverse events and deviations from investigation plan;
- Assess for changes in beta blockers, ACE, ARB, anti-coagulants, anti-platelets, anti-arrhythmics ;

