- Measure and record Nanostim™ LP performance, as described in 6.4.3.3 Nanostim™ LP Assessment and Programming.

Data Submission

Complete and submit the following case report forms and device print outs to St. Jude Medical, Sylmar, CA using the EDC system.

- Follow-up Visit Form (includes medication changes)
- Nanostim™ LP Assessment and Programming Form
- Study Withdrawal Form, if applicable
- Adverse Event Form, if applicable
- Deviation Form, if applicable
- Product Out of Service Form, if applicable
- System Revision Form, if applicable
- Death Form, if applicable
- Healthcare Utilization Form, if applicable

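### Does the undefined high-rate waiver for the capture threshold in section 6.4.3.3 put the primary effectiveness result at risk?

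*Combined protocol and SAP*

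**What the plan says.** Section 6.4.3.3 lists the capture threshold at 0.4 ms among the values to record. Its footnote then says "Capture thresholds are not required if a high" and, after a page break, "ventricular rate is present. Confirm at least three consecutive beats have capture before recording the capture threshold results". No rate, duration or method of establishing the condition is given. The same footnote states the other waiver numerically: "R-wave amplitude measurements are not required if the subject's intrinsic rate has been established to be below 30 beats per minute".

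The clause reaches the primary endpoint. Section 6.2.1.2 reads "A subject will be considered to have met the primary effectiveness endpoint if the pacing threshold voltage is" at most 2.0 V at 0.4 ms, together with an R-wave criterion. Section 6.4.5.5 requires the 6-month visit to record "LP performance, as described in 6.4.3.3". Section 6.4.5.6 does the same for later visits, and so for the 12-month supplementary endpoint.

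On who measures, section 6.4.3.3 says "Investigator and/or sponsor will interrogate the" device, and section 6.4 adds that "Sponsor representatives may assist the investigator in assessing pacemaker effectiveness". The only core laboratory described (section 11.3) reads Holter recordings.

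**The concern.** An endpoint component may be left unmeasured on a condition that each site must interpret for itself. The study has one arm and describes no blinded assessor. Chronic or permanent atrial fibrillation is the first indication listed in section 6.3.1, so the clause may well be used. The contrast with the 30 beats per minute rule suggests that one of two parallel waivers was left unfinished.

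If staff omitted the test more often in subjects whose threshold would have failed, and those subjects were excluded or judged on the R-wave alone, the observed success rate would be too high and a device at the 85% goal could pass too often. If omitted tests were counted as failures, a sound device could lose power. A monitor would have no stated rate against which to check an omission.

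**Working it through.** **Inputs from section 6.2.1.2:** n = 300, performance goal 85.0%, success if the lower limit of the exact two-sided 95% interval exceeds the goal. The power and assumed true rate behind 300 are blacked out, so there is no stated figure to reproduce. **Assumptions, not in the documents:** a waived share w of 1%, 2% or 5% (3, 6 or 15 of 300), and a proportion q of waived subjects whose threshold would have failed.

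**Step 1, pass mark.** The lower limit for x successes is the 2.5th percentile of Beta(x, n − x + 1). For 268/300 it is 0.8528 (pass); for 267/300 it is 0.8490 (fail). The false-pass chance is P(X ≥ 268 | n = 300, p = 0.85) = 0.0183.

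**Step 2, waived subjects excluded, true rate exactly 85%.** The success rate among those measured is

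p_m = (0.85 − w(1 − q)) / (1 − w).

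Example with w = 0.05 and q = 0.30: (0.85 − 0.05 × 0.70)/0.95 = 0.815/0.95 = 0.8579. The sample is 285, the pass mark 255, and P(X ≥ 255 | 285, 0.8579) = 0.041. The other cells follow in the same way, with pass marks 265/297, 263/294 and 255/285:

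| Failure rate among waived (q) | 1% waived | 2% waived | 5% waived |
|---|---|---|---|
| 15% (unrelated to outcome) | 0.022 | 0.017 | 0.018 |
| 30% (twice the base rate) | 0.026 | 0.023 | 0.041 |
| 50% | 0.032 | 0.036 | 0.108 |
| 100% (extreme bound) | 0.053 | 0.096 | 0.548 |

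The first row moves around 0.018 only because the binomial is discrete. Power at a true rate of 92% in that row is 0.965, 0.952 and 0.949, against 0.960 with no waivers.

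**Step 3, what the last row requires.** At a true rate of 85%, 300 × 0.15 = 45 subjects fail. With 5% waived and q = 1, 15 of those 45, one third of all failures in the trial, sit in the waived group and no success does.

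**Step 4, other scoring rules.** If waived subjects would all have failed but are scored on an adequate R-wave alone, the success rate becomes 0.85 + w and the false-pass chance 0.053, 0.131 or 0.692. This is again the extreme bound. If waivers count as failures, the rate is p(1 − w). Power at a true 92% is then 0.876, 0.724 or 0.179, and at a true 95% it is 0.999, 0.994 or 0.742. That rule errs against the device.

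**Step 5, is selection on the reading described?** The condition in 6.4.3.3 is a rhythm present at the visit. No passage describes taking a threshold and then waiving it, and an omitted test gives no value to act on. The supported statement is that unblinded site or sponsor staff judge whether the rhythm condition applies. No passage links a fast ventricular rate to a threshold above 2.0 V, so nothing in the documents points to q near 1.

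**The case for a change.** The best case for a change is that the trigger is visibly undefined in an unredacted section, that its twin is numeric, and that the omitted value helps decide the primary endpoint. A hidden scoring rule would not define the trigger. At 264/300, four subjects rescored as successes (268/300) or excluded (264/296, lower limit 0.8508) would turn a miss into a pass. A definition would cost one sentence.

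The textual facts and the arithmetic stand. The tipping count is weaker than it looks: it holds for any four hidden failures from any cause and says nothing about how often this waiver hides one.

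The documents also work against abuse of the clause. Section 6.4.3.3 requires the pulse amplitude to be kept at a stated multiple of the threshold, so the investigator needs the threshold for patient care. Device printouts are submitted after implant and after each follow-up visit, and section 16.0 provides for source data verification, though the printouts go to the sponsor. Section 6.2.1.2 has thresholds tabulated at every visit, so a missing 6-month value can be seen beside earlier ones. Nothing bars a second attempt within the ±30-day window. Section 14.2 refers to instructions for use for the pacemaker and the programmer link. Neither these nor the Assessment and Programming Form is available here, so it is unknown whether they define the condition or already record the rate.

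The further requests, for a scoring rule and sensitivity analyses, cannot be pressed. Text in 6.2.1.2 and 6.2.1.3 is blacked out, and the public version of 6.2.1.6 may be incomplete.

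**Conclusion.** No change to the plan is called for. This is a missing definition that clinicians can fill sensibly at the bedside, and nothing visible shows that following the plan as written gives a wrong result. Waivers unrelated to outcome leave the false-pass chance at about 2% and power at a true 92% near 0.95. A moderate association (twice the base failure rate) gives at most 4.1% at a 5% waived share. Serious inflation needs both a sizeable waived share and a strong link to failure: 10.8% when 5% are waived and half of them fail, 54.8% when all of them fail.

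The conclusion rests on assumed waived shares of 1% to 5% and on the absence of any documented link between a fast rhythm and a failing threshold. The true frequency, the scoring rule and the content of the form cannot be seen, so neither the direction nor the size of any effect can be established from the documents. Stating what counts as high would be a harmless clarification for the sponsor and investigators to make if they wish, but the validity of the primary analysis does not depend on it.

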6.4.3.4 Nanostim™ LP Repositioning and/or Release

Once the investigator implants the Nanostim™ LP and successfully demonstrates acute effectiveness, the investigator may release the Nanostim™ LP. Investigator may reposition Nanostim™ LP, if necessary. For release and repositioning procedures, refer to the IFU. Once the Nanostim™ LP has been released, investigator will use a retrieval catheter for removal, if needed (Refer to Retrieval Catheter IFU). Once the Nanostim™ LP has been removed, investigator may attempt to implant another Nanostim™ LP, or instead, choose to implant a market-approved pacemaker or ICD. When the investigator has released the Nanostim™ LP, s/he will use fluoroscopy to assess positioning of the implanted Nanostim™ LP.

